7.4.3 Clinical Laboratory Assessments

Blood samples will be collected for the following clinical laboratory tests, following the timing noted in the Schedule of Assessments ([Appendix 1: Schedule of Assessments](#)) and sent to the central laboratory for analysis (Section 7.3.6). All samples should be clearly identified.

CCI

Local clinical laboratory samples will be collected for screening, post-treatment effect and emergency safety evaluations but are not required to be collected/recorded in the CRFs (see Table 3).

Table 3 Local Laboratory Assessments

Screening	Hematology	Lymphocyte count
	Serology	Hepatitis B, Hepatitis C, HIV, VZV**
	Per local guideline, imaging and/or blood test: Chest X-ray, chest CT scan, MRI and/or positive QuantiFERON-TB Gold test and/or skin test	TB (active and/or latent)
	MRI	PML and EC/IC
	Urine and/or serum tests	Pregnancy
Baseline	Hematology	Lymphocyte count to be repeated if interval is more than 4 weeks from screening sample
	Urine and/or serum tests	Pregnancy
Post-treatment (Year 1 and 2)	Hematology	Lymphocyte count at 2, 6, 12, 14, 18, 24 months
Before Year 2 dosing	Hematology	Lymphocyte count
	Serology	Hepatitis B, Hepatitis C, HIV
	Per local guideline, imaging and/or blood test: Chest X-ray, chest CT scan, MRI and/or positive QuantiFERON-TB Gold test and/or skin test.	TB (active and/or latent)
	Urine and/or serum tests	Pregnancy

Abbreviations: CT=computed tomography; HIV=human immunodeficiency virus; MRI=magnetic resonance imaging; PML=progressive multifocal leukoencephalopathy; EC/IC=exclusion criteria/inclusion criteria; TB=Tuberculosis; VZV=Varicella Zoster virus

** Only if the subject has no history of varicella infection or immunity

The total blood volume that will be collected at each visit from each subject for the above mentioned assessments is described in [Appendix 9: Blood Volumes](#).

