3.4 Risk-Benefit Assessment

The safety and tolerability of oral Mavenclad[®] in relapsing remitting MS have been demonstrated from the 2-year CLARITY trial followed by an additional 2.5 years of follow-up from the CLARITY-Extension (Cook S, 2016). While an oral formulation eliminates the adverse effects associated with frequent injections, Mavenclad[®] acts by depleting lymphocytes with a risk of developing opportunistic infections. The Sponsor have put in place adequate risk minimization measures for the participating subjects in this trial as well. Administering Mavenclad[®] will be restricted in subjects with lymphocyte count below normal in Year 1 and at least 800 cells/mm³ before initiating in Year 2. In addition, the lymphocyte count will be monitored at 2 and 6 months after each dosing schedule in Year 1 and Year 2. Subjects will be screened for latent TB infection as per local guidelines, as well as for Hepatitis B, Hepatitis C and human immunodeficiency virus (HIV) infection and will be excluded if found positive before each dosing schedule. The MRI scans will be evaluated by an expert to exclude any PML infection at screening and throughout the trial.

[figure not shown]

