5.4 Criteria for Initiation and Continuing of Trial Treatment

The lymphocyte count must be within normal limits before initiating treatment in Year 1, and at least 800/mm³ before initiating treatment in Year 2. If necessary, the treatment course in Year 2 can be delayed for up to 6 months to allow for recovery of lymphocytes. If this recovery takes more than 6 months, the subject will not receive the trial treatment anymore.

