7.1.9 Month 14 Visit (± 7 days)

- Review of subject diary
- Blood samples for safety analysis at local laboratory*
- Assessment of AEs, SAE's concomitant medications and concomitant procedures

*Lymphocyte count will be checked locally after 2 months of starting treatment. If the lymphocyte count is below 500 cells/mm³, it should be actively monitored until values increase again.

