8.5 Description of Statistical Analyses

8.5.1 General Considerations

All analyses of all endpoints except the primary analysis, will be performed exploratively and, differences with a p-value of 0.05 or less will be considered nominally statistically significant.

Parameter estimates with associated 95% confidence intervals (CIs) will be reported in each analysis. No correction for multiple testing will be applied for any secondary or tertiary analysis.

Subjects' demographic factors and baseline clinical characteristics will be summarized with the following measures: mean with standard deviation, minimum and maximum for normally distributed continuous variables, median with interquartile range, minimum and maximum for other continuous variables and counts with percentages for categorical variables.

As the secondary and tertiary analysis set concerns repeated measurements of outcomes for each individual, it is likely that observations pertaining to each individual will be correlated. Furthermore, as this is a multi-center trial, it is likely that clustering of individuals within trial sites will produce an additional source of correlation. Mixed-effects regression, whereby a three-level hierarchical model is specified for observations within subjects within trial sites, will be used to account for within-subject and within-center correlation (Gibbons, 2010).

The parametric assumptions underlining the regression models specified will be examined. Should these assumptions be violated, alternative methods, such as non-parametric approaches, may be considered in addition.

Assessment Schedules

It is likely that the second year treatment may be delayed substantially due to grade 3 or 4 lymphopenia for a small number of subjects for whom the second dose is not required immediately. Due to the need for a finite follow-up period, a buffer of 3 months is given for subjects who do not receive the second treatment at the specified time. Subjects for whom treatment is delayed by over 3 months may not have all assessment data captured and as such, these observations will be treated as missing in efficacy analyses.

In each analysis, should assessment be delayed, subjects' assessment data will be treated as though it occurred at the time point specified and inferences will be conducted accordingly.

Missing Data

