Assessments	Pre-baseline Screening	Baseline	Month 1	Month 2	Month 3	Month 6	Month 12	Month 14	Month 15	Month 18	Early termination/ Month 24
Visit windows	Up to -3 months	+7 days	±7 days	±7 days	±7 days	±7 days	±7 days	±7 days	±7 days	±7 days	±7 days
Informed consent ¹	X										
Demographics, medical history	X										
Inclusion/exclusion criteria	X	X									
Weight ² / Cladribine Tablets dispensed		X	X				X				
IRT contacted	X	X	X				X				
Trial medication administered at site		X	X				X				
Physical examination ³	X	X				X	X			X	X
Lymphocyte count ⁴	X			X		X	X	X		X	X
Serology ⁵	X						X				
TB (active, latent) ⁶	X						X				
Urine pregnancy test ⁷	X	X					X				
MRI	X	X	X	X	X	X	X		X	X	X
CCI											
Disability (EDSS/KFS)	X	X				X	X			X	X
Disability (9HPT)	X	X				X	X			X	X
Disability (T25FW)	X	X				X	X			X	X
Cognition (SDMT)		X				X	X			X	X
Relapse count ⁹		X					X				X
Adverse events, concomitant medications and procedures ¹⁰	X	X	X	X	X	X	X	X	X	X	X
Collection and review of subject diary ¹⁰		X	X	X	X	X	X	X	X	X	X

Abbreviations: 9HPT=9-Hole Peg Test; EDSS=Expanded Disability Status Scale; KFS= Kurtzke Functional System; IRT=interactive response technology; MRI=magnetic resonance imaging; SDMT=Symbol Digit Modalities Test; T25FW=Timed 25-Foot Walk; TB=tuberculosis

1. Informed Consent should be obtained prior to any trial-specific assessments are undertaken
2. Weight to be measured before each treatment course for calculating appropriate dose of cladribine
3. Includes vital signs (blood pressure, heart rate, body temperature)

4. To be done at a local laboratory. If the lymphocyte count at screening is done before 4 weeks from Baseline, it should be repeated within 4 weeks of Baseline. Lymphocyte count should be (i) normal before initiating cladribine in year 1, (ii) at least 800 cells/mm³ before initiating in year 2 (iii) checked at 2 and 6 months after start of treatment in each treatment year. If necessary, the treatment course in year 2 can be delayed for up to 6 months to allow for recovery of lymphocytes. If this recovery takes more than 6 months, cladribine treatment should be terminated
5. To be done at a local laboratory. Serology test for HIV, Hepatitis C, Hepatitis B to be done at screening and at month 12, and varicella to be done at screening. Subjects with a negative varicella serology will be included after 4 to 6 weeks of receipt of varicella vaccination.

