- 1 year = 365.25 days.

Time window

- Day 1 is the day of start of study medication, the day before is Day - 1 (no Day 0 is defined),
- Study day / Treatment day is defined relative to Day 1.

The Visit schedule is defined as follows:

- 1 month = 30 days,
- 1 year = 360 days,

relative to the start date of the Baseline Visit for Treatment Course 1 and relative to the start date of the Month 12b Visit as defined in the eCRF (see also Section 15.3) for Treatment Course 2.

In each analysis, should assessments be delayed, subjects' assessment data will be treated as though it occurred at the time point specified (i.e., out of Visit windows will be not excluded or adjusted for any analyses) and inferences will be conducted accordingly. Thus, further time windows will not be specified.

All observations from unscheduled Visits will be included only in the analyses of Visit independent summaries (e.g. counts of events, progressions or worst value during Treatment Period) unless for the unscheduled Visits prior to start of study medication and the last assessment available. In case of unscheduled Visits prior to start of study medication, these will be considered to define Baseline. In the last missing case the ET Visit will be imputed by the unscheduled Visit.

The assessments of the ET Visit will be mapped to the nearest planned post-Baseline Visit with a missing assessment before or after the ET Visit of the individual assessment for all statistical analyses and descriptive summaries. As not all assessments of the ET are performed at each Visit, the different assessments of the ET can be assigned to different Visits. If the duration (in days) between the ET Visits and two missing planned Visits are equal, then the assessment will be assigned to the later Visit.

Handling of missing data

Unless otherwise specified in respective sections, missing data will not be replaced.

The handling of missing covariate and stratification factor information is described below.

The handling of missing DMD end date is described in Section 12.

Incomplete or missing onset dates of relapses from "MS Relapse Report" will be imputed as follows:

- In cases where the onset date is partially missing but the onset month and year, or the onset year are equal to the start of study medication or the date is missing then the onset date will be replaced by the start date of study medication.

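### The protocol sets Year 2 lymphocyte checks by time since dosing but schedules them by study month, and does not say which governs, or which pre-dose tests must be current, when Course 2 is delayed by up to 6 months

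*Protocol*

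**What the plan says.** **Set by time since dosing.** Protocol 3.4 says "the lymphocyte count will be monitored at 2 and 6 months after each dosing schedule in Year 1 and Year 2". Section 5.2 says the same in other words. Appendix 1 footnote 4, attached to the lymphocyte row, requires the count to be "checked at 2 and 6 months after start of treatment in each treatment year". The note under the Month 14 visit (7.1.9) reads "Lymphocyte count will be checked locally after 2 months of starting treatment", and the Month 18 note (7.1.11) gives the 6-month equivalent.

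**Set by study month.** Table 3 lists "Lymphocyte count at 2, 6, 12, 14, 18, 24 months". The Appendix 1 grid marks lymphocyte counts at Months 14, 18 and 24 with a ±7-day window, and none at Month 15.

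**Permitted delay.** Section 5.4 states that "the treatment course in Year 2 can be delayed for up to 6 months to allow for recovery of lymphocytes". Section 7.1.8 and footnote 4 repeat this.

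**Tests ahead of Course 2.** Table 3 lists lymphocyte count, serology, TB and pregnancy tests as due ahead of the second-year course. Section 7.1.8 and the Appendix 1 grid place them at the Month 12 visit; footnote 5 says "Serology test for HIV, Hepatitis C, Hepatitis B to be done at screening and at month 12". Weight and tablet dispensing for Year 2 also appear only at Month 12 in the grid, and Section 6 ties Year 2 IRT dispensing to registration of that visit.

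**Follow-up.** Protocol 8.5.1 says "a buffer of 3 months is given for subjects who do not receive the second treatment at the specified time".

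**SAP.** Section 9 counts the Course 2 visit schedule "relative to the start date of the Month 12b Visit as defined in the eCRF". Section 13 takes the Course 2 weight from the same visit. No Month 12b Visit appears in the protocol.

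**The concern.** A subject whose lymphocytes recover slowly after Course 1 may be re-dosed months after the Month 12 visit. Severe lymphopenia is an identified risk in Section 3.3, and the protocol's responses to counts below 500 and below 200 cells/mm³ need a count to prompt them. A site following the study-month grid could take the Month 14 count before the dose whose effect it is meant to detect.

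The same delay ages the Month 12 tests. Section 3.4 says subjects are excluded if found positive ahead of each course. Section 5.5.1 makes pregnancy, and HIV infection, active TB or active hepatitis found before Course 2, mandatory reasons for withdrawal. For Course 1 the protocol protects currency: the lymphocyte count is repeated if it is more than 4 weeks old, and the pregnancy test is repeated at Baseline. No equivalent is written for serology, TB or pregnancy at a delayed Course 2.

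**Working it through.** **Inputs.** Checks due 2 and 6 months after each course starts (3.4, 5.2, Appendix 1 footnote 4). Scheduled Year 2 counts at Months 14, 18 and 24, ±7 days (Table 3, Appendix 1). Delay d from 0 to 6 months (5.4). Buffer of 3 months (8.5.1). Visit month of 30 days (SAP 9).

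**Reproducing the schedule.** With course starts at Months 0 and 12, adding 2 and 6 gives Months 2, 6, 14 and 18. These match Table 3, so the two rules agree when d = 0.

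**Reading A: months fixed from Baseline.** Course 2 starts at Month 12 + d. The checks are due at 14 + d and 18 + d. The scheduled counts fall at 14 − (12 + d) = 2 − d, 18 − (12 + d) = 6 − d and 24 − (12 + d) = 12 − d months after the start. Month 12 tests are d months old at dosing.

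| Delay d (months) | Course 2 starts at Month | Checks due at Months | Month 14 / 18 / 24 counts, months after start | Age of Month 12 tests (months) |
|---|---|---|---|---|
| 0 | 12 | 14, 18 | 2 / 6 / 12 | 0 |
| 1 | 13 | 15, 19 | 1 / 5 / 11 | 1 |
| 2 | 14 | 16, 20 | 0 / 4 / 10 | 2 |
| 3 | 15 | 17, 21 | −1 / 3 / 9 | 3 |
| 4 | 16 | 18, 22 | −2 / 2 / 8 | 4 |
| 5 | 17 | 19, 23 | −3 / 1 / 7 | 5 |
| 6 | 18 | 20, 24 | −4 / 0 / 6 | 6 |

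- The Month 14 count falls before dosing once the delay exceeds 60 days, or 53 to 67 days allowing for the ±7-day window.
- Among whole-month delays, only d = 4 places a scheduled count at the 2-month point, because Month 18 happens to land there. At d = 1, 2, 3, 5 and 6 none does.
- At d = 6 the only scheduled count after the dosing day is the one at 6 months.

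**Reading B: months counted from Month 12b.** The Month 14 and 18 checks fall 2 and 6 months after the Course 2 start for every d. In study time they are at Months 17 and 21 for d = 3, and 20 and 24 for d = 6. The final visit moves to 24 + d: Month 27 for d = 3 and Month 30 for d = 6. The 3-month buffer reaches 24 + 3 = Month 27, so any delay beyond 3 months runs past it.

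**Pre-dose tests.** The ages in the last column hold under both readings, because Reading B moves the visits after Course 2 and not the Month 12 tests.

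**The case against.** The case against is substantial. Reading A is not stated anywhere. The Month 14 and 18 notes refer to time since treatment, and Section 5.2 describes Months 15, 18 and 24 as following the second course. The SAP adopts Reading B and cites the eCRF for it. Unscheduled visits allow laboratory retesting (7.1.13), counts below 500 must be followed until they rise, and additional pregnancy tests are permitted where country rules require them (7.1.1). The protocol also defers to the SmPC for dosing and precautions, and that document is not available here. The stated consequence of the 3-month buffer is confined to efficacy analyses; SAP 7 keeps all safety data.

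This makes the size conditional but does not remove the conflict. An analysis plan does not instruct sites. The study months with ±7-day windows are in the protocol, and Section 8.5.1 itself says that subjects delayed by more than 3 months may not have all assessments captured.

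Three stronger readings are tempting and should not be drawn:

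- *That the SAP's Month 14 and 18 lymphocyte summaries mix pre-dose and post-dose values.* For subjects who start Course 2, SAP 15.3 assigns every count from the Month 12 Visit up to the Course 2 start to Month 12, Month 12b or an unscheduled visit.
- *That Appendix 1 removes the early post-dose check.* Footnote 4 still requires it. In a delayed subject the check is required but may have no scheduled visit.
- *That the pre-dose lymphocyte count can be 6 months old in a subject waiting to recover.* Recovery to at least 800 cells/mm³ is a condition of dosing, and SAP 15.3 provides for repeat counts.

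**Conclusion.** The concern holds as an unreconciled conflict within the protocol, and between the protocol and the SAP's visit anchor. If months are fixed from Baseline, the Month 14 count is on or before the dosing day for delays of 2 months or more, and most whole-month delays leave the 2-month check without a scheduled visit. If months are counted from Month 12b the post-dose checks are correctly timed, but the protocol does not define that visit, and delays beyond 3 months outrun the buffer. Under either reading, Year 2 serology, TB and pregnancy results can be up to 6 months old at dosing and still meet Table 3, which gives no maximum age.

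The number of subjects affected cannot be worked out. Section 8.5.1 expects a substantial delay in only a small number. The pre-dose test point rests on the protocol being silent about repeats; the SmPC might require them. The point deserves correction because it concerns slow-recovering subjects who are re-dosed, and because the remedy is cheap.

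**What to change.** Reconcile Protocol 3.4, 5.2, 6 (IRT dispensing), 7.1.8 to 7.1.12, Table 3, Appendix 1 and 8.5.1 with the SAP's Month 12b Visit, so that the protocol:

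1. states one anchor for Year 2 safety visits;
2. shows the delayed-start visit in the schedule, including where weight and dispensing take place;
3. says which of the tests listed ahead of Year 2 dosing must be current at the actual Course 2 start;
4. explains how the 3-month buffer fits a permitted delay of 6 months.

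The choice of anchor and of test validity is a clinical one for the sponsor. The SAP's lymphocyte visit labels need no change, since Sections 9 and 15.3 already handle them.

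The cost is amendment wording, one schedule column, and at most repeat routine local tests in the delayed subjects.

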5.3 Selection of Trial Population

Only subjects meeting all inclusion criteria and no exclusion criteria will be enrolled into the trial as subjects. Prior to performing any trial assessments not part of the subject's routine medical care, the Investigator will ensure that the subject has provided written informed consent following the procedure described in Section 9.2.

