5.3.1 Inclusion Criteria

To be eligible for inclusion into this study, the subjects must fulfill all of the following criteria:

1. Subjects must voluntarily give written informed consent. Subjects must read and fully understand the Informed Consent Form (ICF) and the requirements of the trial and must be willing to comply with all trial visits and assessments
2. Male or female subjects ≥ 18 years old
3. Highly active relapsing MS as defined by:
 - One relapse in the previous year and at least 1 T1 Gd+ lesion or 9 or more T2 lesions, while on therapy with other DMDs.
 - Two or more relapses in the previous year, whether on DMD treatment or not
4. EDSS score ≤ 5.0
5. Female subjects of child-bearing potential must use highly effective methods of contraception to prevent pregnancy for 4 weeks before initiation of Mavenclad[®] and must agree to continue to practice adequate contraception for at least 6 months after the last dose (see [Appendix 12: Birth control methods which may be considered as highly effective](#)). A woman is considered of child-bearing potential (WOCBP), i.e. fertile, following menarche and until becoming post-menopausal unless permanently sterile. Women using systemically acting hormonal contraceptives should add a barrier method during Mavenclad[®] treatment and for at least 4 weeks after the last dose in each treatment year.
6. WOCBP must not be pregnant nor lactating or breast-feeding at Screening through at least 1 week after the last dose
7. Male subjects must be willing to use a condom in addition to having their female partner use another form of contraception (such as an intra-uterine device [IUD], barrier method with spermicide, or hormonal contraceptive [e.g., implant, injectable, patch or oral]) from Baseline until 6 months after the last dose of Mavenclad[®], unless their partners are infertile or surgically sterile.
8. Subjects who test positive for Varicella Zoster virus (VZV) will be included. In case of negative serology, the subject may be included after 4 to 6 weeks of receiving VZV vaccination.

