7.1 Schedule of Assessments

7.1.1 Pre-Baseline Screening (-3 months)

During the pre-Baseline screening visit, the prospective subject will be informed of the trial objectives and overall requirements, and written informed consent will be obtained prior to any trial specific assessments (see Section 9.2). The subject will then undergo a clinical MRI assessment centrally for disease activity and also to rule out PML. The read-out of this MRI scan to ensure compliance with the inclusion and exclusion criteria will be at investigator discretion (see Section 5.3).

A complete Screening Evaluation is to be performed during 3 months from Baseline, which will include the following assessments:

- Signing informed consent form
- Register IRT for shipment of medication to the site
- Demographic data, including date of birth, gender and race
- Medical history
- Disease history, including classification of disease, number of relapses within the past 12 months, treatment history, diagnosis date
- Review of inclusion/exclusion criteria
- Physical examination, including vital signs (including blood pressure, heart rate, temperature), height and weight
- Serology (HIV, Hepatitis C and B, and Varicella Zoster virus) and TB test
- MRI assessment (see Section 7.3.1)
- Neurological assessment including EDSS/KFS, 9HPT and T25FW (excluding SDMT) (see Section 7.3.2)
- The contraceptive method used will be recorded, or, alternatively, if applicable, the age at menopause will be documented
- Blood samples for safety analysis at local laboratory (see Section 7.4.3)*.
- Urine pregnancy test (for female subjects of child-bearing potential only) at local laboratory**
- Assessment of AEs, concomitant medications and concomitant procedures

*** If the local laboratory blood at the Screening visit is conducted within 10 days of Study Day 1, no blood samples need to be repeated at Study Day 1.**

****Additional serum or urine pregnancy tests will be permitted throughout the trial period as required by country specific regulations.**

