12.9 Appendix 9: Blood Volumes

Core trial (n=265 subjects)

Local laboratory analysis

Lymphocyte count	1	7	Pre-Baseline, end of Months 2,6,12,14,18,24	7
Serology	3.5	2	Pre-Baseline and end of Month 12	7
TB (Quantiferon test)**	3	2		6
Varicella serology**	3	1	Pre-Baseline	3
Total	Maximum 25.5	-		108

*Baseline, and end of Month 3, 6, 12, 15, 18 and 24 for all above panel except NFL at Baseline, and end of Month 12 and 24 **In case, investigator decides to test for Latent TB by Quantiferon test or decides to test varicella serology if subject provide no prior history of varicella infection

CCI

CCI

CCI

12.10 **Appendix 10: Example of Subject Diary**

Subject Diary Card: Week ___ to ___

Patient Initials:

Patient Number:

Dear Subject,

Please complete this diary card (with a pen) for each daily dose of study drug and always take it with you to the hospital when you visit.

Please also remember to **bring your unused study drug** with you in their original containers. You will also need to **bring back the blister packs and boxes from your used study drug.**

This diary has also been designed to help us follow your **general health and any problem or discomfort you may experience** while you are at home and to record **all medication** you take additionally to the study drug.

Start Date	Stop Date	List any new medications or changes in the medications	Specify reason for taking any specific concomitant medication. All medications, drug should be listed here e.g. OTC or painkillers... as well.

Subject Study Drug Medication Record

Week	Date	Time (circle am or pm)	Number of tablets taken	Kit #	Comments***
		am			
		pm			
		am			
		pm			
		am			
		pm			
		am			
		pm			
		am			
		pm			
		am			
		pm			

Week	Date	Time (circle am or pm)	Number tablets taken	of Kit #	Comments***
		am			
		pm			
		am			
		pm			
		am			
		pm			
		am			
		pm			
		am			
		pm			
		am			
		pm			
		am			

Week	Date	Time (circle am or pm)	Number of tablets taken	Kit #	Comments***
		pm			
		am pm			
		am pm			
		am pm			

Comments *** If a tablet was missed, please record the date and reason for missed dose

SYMPTOMS RECORD		
Start Date	Stop Date	Briefly list any problem or discomfort you experienced (use as many lines as necessary)

CCI

CCI

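### Inclusion 8 can be met only with a VZV serology result, but the Table 3 footnote calls for that test only in subjects without a varicella history, so some subjects handled under Table 3 fit neither entry route

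*Protocol*

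**What the plan says.** - **Protocol 5.3** makes eligibility all-or-nothing: "Only subjects meeting all inclusion criteria and no exclusion criteria will be enrolled into the trial as subjects".
- **Protocol 5.3.1, criterion 8** gives the first route as "Subjects who test positive for Varicella Zoster virus (VZV) will be included" and the second as "In case of negative serology, the subject may be included after 4 to 6 weeks of receiving VZV vaccination". It mentions no route based on history.
- **Protocol 7.1.1** lists among the screening procedures "Serology (HIV, Hepatitis C and B, and Varicella Zoster virus) and TB test", with no condition attached.
- **Protocol Appendix 1, footnote 5** (schedule of assessments) also has no condition: "and varicella to be done at screening". It repeats the vaccination route: "Subjects with a negative varicella serology will be included after 4 to 6 weeks of receipt of varicella vaccination".
- **Protocol 7.4.3, Table 3** lists VZV under screening serology with a footnote: "Only if the subject has no history of varicella infection or immunity".
- **Protocol Appendix 9** (blood volumes) marks the varicella sample as conditional, drawn where the investigator "decides to test varicella serology if subject provide no prior history of varicella infection".

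**The concern.** The criterion needs a laboratory result that the laboratory table does not ask for in every subject. A site working from Table 3 would draw no VZV sample from someone who reports past chickenpox or vaccination, and would then have nothing with which to tick Inclusion 8. A site working from the schedule would test the same person. Both could point to protocol text in support.

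Two things are at stake. The first is a clean eligibility record: a treated subject with no result has an unmet inclusion criterion. The second is a pre-dose safety check. Cladribine depletes lymphocytes (Section 3.4), and Section 3.3 names herpes zoster among the important identified risks. Section 5.5.1 lists zoster reactivation as a reason to consider withdrawing or delaying the second course. Serology is how the protocol finds subjects who need vaccination before dosing. An unverified history that turns out to be wrong would bypass that step, and the protocol does not say what evidence of history or immunity is enough.

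**Working it through.** The plan gives no figure to reproduce here. The check is a comparison of the passages, followed by one piece of arithmetic on timing.

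**Step 1: what each passage requires**

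| Place | Is VZV serology called for? |
|---|---|
| Inclusion 8 (mandatory under 5.3) | A result is needed for either route |
| Section 7.1.1 | Yes, in all subjects |
| Appendix 1 footnote 5 | Yes, in all subjects |
| Table 3 footnote | Only where there is no history of infection or immunity |
| Appendix 9 note | By investigator decision, where there is no history of infection |

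**Step 2: follow each kind of subject through the text**

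1. No history, tested, positive: meets the first route.
2. No history, tested, negative, vaccinated, waits 4 to 6 weeks: meets the second route.
3. Reported history, tested because the site follows Section 7.1.1 or Appendix 1: has a result, so Inclusion 8 can be met.
4. Earlier positive serology on record, not retested under Table 3: can reasonably be said to have tested positive, since Inclusion 8 does not say the test must be done within the trial.
5. Reported infection or vaccination, no serology result, not tested under Table 3: neither positive nor negative, so neither route is met as written.

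Only case 5 fails.

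**Step 3: can the passages be read together?** The Table 3 footnote could be taken as qualifying the schedule. That reconciles it with Section 7.1.1 and Appendix 1, but Inclusion 8 would still need a result. If instead the schedule governs, the Table 3 footnote is wrong. Either way, one text has to change.

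**Step 4: is there time to test everyone?**

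- Screening limit: up to 3 months, taken as 90 days (an assumption), plus the 7-day Baseline window in Section 7: 90 + 7 = 97 days.
- Post-vaccination wait: 4 weeks = 28 days; 6 weeks = 42 days.
- Time left for the test, the result and the vaccination: 97 − 42 = 55 days, or 97 − 28 = 69 days.

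The wait therefore fits inside the screening period, and one re-screening is allowed (Sections 5.2 and 7.1.1).

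**Step 5: effect on the analyses.** SAP 8.2 defines the ITT set by medication assignment in the iRT system and the FAS by having received at least one dose. SAP 9 keeps all data regardless of protocol deviations, except MRIs taken during steroid treatment. An unmet Inclusion 8 removes no one from the primary analysis.

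**The case against.** The best defence is that Table 3 says when the test is called for and does not forbid it. Section 7.4.3 itself ties blood sampling to the Appendix 1 schedule, and that schedule has the test at screening. The dead end arises only if a site lets a table footnote override the schedule. This stands, and it limits the point to sites that work from Table 3. It does not remove the conflict, because the footnote is current operative text.

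The amendment rationale in Appendix 15 says the criterion was added to admit subjects with previous exposure and immunity. That suggests a drafting omission in Inclusion 8 rather than an intention to test everyone. It is evidence of intent but not an operative rule, and it bears on which fix to choose.

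Three stronger readings are tempting, and the documents do not support them:

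- A reader might infer that every subject with a varicella history or known immunity is ineligible. An earlier positive serology can satisfy the first route.
- A reader might count the Appendix 9 note as a further eligibility rule. It explains which volumes in a blood-volume table are conditional. It repeats the conflict but sets no entry criterion.
- A reader might infer that the SAP would miss these cases, because SAP 15.3 lists only non-compliant positive serology results and for VZV a positive result is the compliant one. However, SAP 8.1 and 10.2.1 already provide for reporting inclusion and exclusion deviations.

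**Conclusion.** The inconsistency is real and should be corrected. A subject with reported infection or vaccination and no serology result, handled under Table 3, cannot meet Inclusion 8 as written. If the reported history is wrong and unverified, that subject also misses the vaccination step.

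The size is limited. The documents give no rate of varicella history or of mistaken history, so the number affected is unknown, and no harm to any subject is shown. No estimate, test or analysis set changes. What remains is a conflicting instruction on a pre-dose safety check, across approximately 80 sites, with possible eligibility deviations.

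The conclusion rests on two readings: that being included on a test means having a result, from the trial or earlier; and that a site may reasonably take the Table 3 footnote as its instruction. Whether a history may properly replace a test depends on the SmPC, which is not among the documents.

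**What to change.** **Preferred: test everyone.** Delete the Table 3 condition on VZV and the varicella clause in the Appendix 9 note, so that every subject has a VZV serology result before the first dose. These are two deletions. The cost is one 3 mL sample already listed in Appendix 9, plus the 4 to 6 week wait after vaccination for any subject found seronegative, which fits the screening limit as shown above.

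**Alternative: accept documented history.** If the SmPC permits, and in line with the amendment rationale, amend Inclusion 8, Section 7.1.1 and Appendix 1 footnote 5 to accept documented infection or immunity in place of the test. State what counts as documentation, and align Appendix 9 with Table 3. These are four edits, and the cost is reliance on records instead of a result.

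Either change touches eligibility or testing, so it may need authority and ethics committee approval (Section 10.5). It helps only while subjects are still being screened.

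**Optional in the SAP.** The SAP 15.3 listing could be extended to VZV results that are negative or not done, with vaccination status. Its value is doubtful: Section 7.4.3 does not require local results to be recorded in the CRF, so untested and unrecorded subjects might look alike. SAP Table 1 does list varicella serology, and eligibility deviations are already reported elsewhere.
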